13.1.6.3 Clinical Laboratory Evaluations

Descriptive summaries (mean, SD, median, minimum, and maximum) of actual (absolute) values and changes from baseline values will be presented for clinical laboratory values for each treatment group at each time point in each period.

The number of subjects with clinical laboratory values categorized as below, within, or above normal ranges will be tabulated showing change from baseline (shift tables) for each clinical laboratory parameter by treatment group and by study visit in each period.

Laboratory values that are outside the normal range will also be flagged in the data listings and presented with the corresponding normal ranges. Any out-of-range values that are identified by the investigator as being clinically significant will also be shown in a data listing.

13.1.6.4 Vital Signs

Descriptive summaries (mean, SD, median, minimum, and maximum) of actual values and changes from baseline will be calculated for systolic blood pressure (SBP), diastolic blood pressure (DBP), and pulse for each period.

The number of subjects with vital signs values categorized as below, within, or above normal ranges will be tabulated showing change from baseline (shift tables) for each parameter by period, by treatment group and by study visit. Pre- and post-treatment values may also be presented with an analysis of mean changes from baseline.

13.1.6.5 Twelve-lead Electrocardiograms

The number and percentage of subjects with normal and abnormal ECG findings will be summarized for each treatment group at each time point in each period. Abnormal results will be grouped as clinically significant and not clinically significant.

A comparison of QT results will be presented. Summary statistics will be displayed by period, by treatment group, and by visit for QT and the QT interval corrected for heart rate (QTc) calculated using Fridericia's QT correction methods.

Descriptive summaries (mean, SD, median, minimum, and maximum) will be presented for ECG measures of PR interval, QRS interval, QT interval, QTcF interval (Fridericia's correction methods), and HR for each treatment group at each time point in each period.

13.1.6.6 Physical Examination Findings

The number and percentage of subjects with normal and abnormal findings in the complete physical examination will be displayed for each treatment group in each period.

13.1.7 Interim Analysis

No interim analyses are planned.

13.2. Sample Size Determination

Accounting for a 20% drop-out/nonevaluable rate, a total sample size of 120 subjects randomized in a 1:1:1 ratio to 2 active trifarotene cream HE1 arms and a vehicle cream arm will provide >80% power to detect a difference between each separate trifarotene cream HE1 arm (32 evaluable subjects) and the vehicle cream arm (32 evaluable subjects) 2-sided Fisher's Exact Test assuming a 70% success rate and a 40% success rate, respectively. This study is not powered to detect a difference between the 2 active arms.

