13. STATISTICS

13.1. Statistical Analysis

This section presents a summary of the planned statistical analyses. A SAP that describes the details of the analyses to be conducted will be written prior to database lock.

Unless otherwise indicated, all testing of statistical significance will be two-sided, and a difference resulting in a P value of ≤ 0.05 will be considered statistically significant.

Summary statistics will be provided for the variables described below. For continuous variables, these statistics will include the number of subjects, mean, standard deviation (SD), median, minimum, and maximum. For categorical variables, these statistics will include the number and percentage of subjects in each category.

The primary analysis period is the first 90 days of treatment (i.e., the Double-blind Period). Overall unblinding will take place at the end of the Double-blind Period of the study only after the database is locked. A second analysis will take place for endpoints assessed from Day 90 through the OLE

Period. The baseline for the safety and efficacy parameters will be measured at Visit 1 or Visit 2, per the Schedule of Events for both the Double-blind Period ([Table 2-1](#)) and OLE ([Table 2-2](#)).

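### The stated power of more than 80% is wrong: 32 v 32 evaluable subjects, two-sided Fisher's exact test, 70% v 40% gives about 62%

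*Protocol*

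**What the plan says.** Protocol Section 13.2 gives a complete sample size statement:

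- Size and allocation: 120 subjects in all, split equally over two active arms and vehicle.
- Loss: "Accounting for a 20% drop-out/nonevaluable rate".
- Claim: the design "will provide >80% power to detect a difference between each separate trifarotene cream HE1 arm (32 evaluable subjects"), with 32 assumed on vehicle as well.
- Test and assumed rates: "2-sided Fisher's Exact Test assuming a 70% success rate and a 40% success rate, respectively".

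The statement names no significance level. Section 13.1 supplies one for the whole protocol: "all testing of statistical significance will be two-sided", and "a difference resulting in a P value of ≤ 0.05 will be considered statistically significant", unless otherwise indicated. Section 13.2 indicates nothing else.

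The Section 2.1 synopsis repeats the power sentence under sample size determination. It also stands in the synopsis of the adult-and-adolescent version (Amendment 2) in the same file.

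**The concern.** A 30-point difference around 55% with 32 subjects per arm is a modest design, and Fisher's exact test is conservative at this size. More than 80% power looked too high. Every input is stated, so the figure can be checked directly.

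The power figure tells the sponsor, ethics committees and readers how to weigh a non-significant comparison. If they believe that the chance of missing the assumed effect is under 20% when it is nearly twice that, they may read too much into a dose that fails to separate from vehicle. Section 7.3 says that the study is meant to find which of the two doses is most effective, so such a reading is possible.

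**Working it through.** **Inputs, all from the protocol**

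| Input | Value | Section |
|---|---|---|
| Randomized | 120, 1:1:1, so 120/3 = 40 per arm | 13.2 |
| Loss | 20% | 13.2 |
| Evaluable | 32 per arm | 13.2 |
| Success rates | 70% active, 40% vehicle | 13.2 |
| Test | two-sided Fisher's exact | 13.2 |
| Significance level | 0.05, two-sided | 13.1 |

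**Step 1: the evaluable number.** 40 × (1 − 0.20) = 32. This agrees with the protocol.

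**Step 2: power of the stated test.** Let X be the successes among 32 active subjects and Y those among 32 vehicle subjects. Exact power is the sum of P(X = x) × P(Y = y), with X ~ Bin(32, 0.70) and Y ~ Bin(32, 0.40), over all tables (x, y) with a two-sided Fisher p ≤ 0.05. The sum is **0.619**. The stated figure of more than 0.80 is not reproduced, and the miss rate is 1 − 0.619 = 0.381.

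**Step 3: check by hand with the normal approximation.**

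- Standard error under the null, with mean rate 0.55: √(2 × 0.55 × 0.45 / 32) = 0.1244.
- Standard error under the alternative: √((0.21 + 0.24) / 32) = 0.1186.
- Pooled test: Φ((0.30 − 1.96 × 0.1244) / 0.1186) = Φ(0.474) = 0.682.
- With a continuity correction of 1/32 = 0.031: Φ((0.30 − 0.031 − 0.2438) / 0.1186) = Φ(0.211) = 0.583.

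The exact Fisher result of 0.619 lies between the two.

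**Step 4: does another method or sample size give more than 80%?** 70% v 40%, level 0.05:

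| Method | 32 per arm | 40 per arm (no drop-out) |
|---|---|---|
| Fisher, two-sided | 61.9% | 72.5% |
| Pooled normal, two-sided | 68.2% | 78.0% |
| Arcsine, two-sided | 68.8% | 78.3% |
| Uncorrected chi-square, exact power, two-sided | 71.3% | 79.6% |
| Unpooled normal, two-sided | 71.6% | 80.7% |
| Fisher, one-sided | 71.4% | 79.8% |
| Uncorrected chi-square, exact power, one-sided | 79.5% | 85.7% |

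At 32 per arm no two-sided entry exceeds 72%, and no one-sided entry reaches 80%. Pooling both active arms (64 v 32, Fisher) gives 78.9%.

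**Step 5: what would give 80% with the stated test.**

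- More subjects at 70% v 40%: 47 per arm gives 78.6% and 48 gives 80.05%. With 20% loss, 48/0.8 = 60 randomized per arm, or 180 in all, against the planned 120.
- A larger effect at 32 per arm, vehicle 40%: active 76% gives 79.7% and active 77% gives 82.2%.

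**Step 6: precision of the planned design.** The 95% CI half-width at 70% v 40% is 1.96 × √(0.45/32) = 1.96 × 0.1186 = 0.232, about 23 percentage points.

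**The case against.** The best defence is that the sizing test is not the primary analysis. Section 13.1.4 makes ITT, with all randomized subjects, the primary population, and Section 13.1.4.2 specifies logistic regression. Sizing on a simple two-proportion test and then fitting a model is ordinary practice, and that part stands. It does not rescue the sentence, which ties its power to Fisher's test on 32 evaluable subjects. Fisher's test on all 40 per arm still gives only 72.5%.

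It is also true that some calculations exceed 80%: the unpooled normal approximation at 40 per arm (80.7%), a one-sided chi-square test at 40 per arm (85.7%), and both active arms pooled with no drop-out, 80 v 40 by Fisher (86.6%). So it would be wrong to say that no calculation can reach 80%. Each of these drops the stated 32 evaluable subjects, and each also changes the test, its sidedness or the separate-arm comparison. None supports the sentence as written.

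A reader might go further in two directions that the documents do not support:

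- **That a negative result will be misread, or a dose dropped.** The protocol sets no go/no-go or dose-dropping rule tied to significance, and the dose for the open-label extension is fixed in advance. Over-interpretation is a risk, not a planned step.
- **That ITT power is about 51%.** This comes from counting every drop-out as a failure: 0.8 × 70% = 56% v 0.8 × 40% = 32%, at 40 per arm. The protocol states no such rule. The missing-data method it names is multiple imputation as a sensitivity analysis (Section 13.1.4.5), with details left to the SAP.

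Finally, a phase 2 trial in a rare disease may reasonably have 62% power. That is an argument for keeping the size, not for stating a different figure.

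**Conclusion.** Wrong as written. With the protocol's own inputs, the power for each active arm v vehicle is 61.9%, against a stated figure above 80%. The shortfall is at least 18 percentage points, too large for rounding or a choice of software. If the assumed 70% v 40% is true, each comparison misses it about 38% of the time.

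The result rests on the two-sided 0.05 level in Section 13.1 applying to the power statement, as nothing else is indicated, and on exactly 32 evaluable subjects per arm. It says nothing about the power of the ITT logistic model, which depends on missing-data handling that the protocol leaves open. It does not show that the trial is too small for its purpose, only that its stated power is not the power it has.

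**What to change.** Keep the sample size. Wherever the sentence appears (Section 13.2, the Section 2.1 synopsis, and the adult-and-adolescent synopsis if that version is still in use), replace the claim of more than 80% power with wording such as:

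*32 evaluable subjects per arm give about 62% power (two-sided Fisher's exact test, alpha 0.05) for 70% v 40%. With vehicle at 40%, at least 80% power requires an active success rate of about 77% (82% power; 76% gives 79.7%). The 95% CI half-width for the difference is about 23 percentage points at 70% v 40%.*

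The 77% is back-calculated from the sample size and should be presented as the detectable rate, not as an expected one. If the sponsor prefers to keep a claim of at least 80% at 70% v 40%, it needs about 48 evaluable, or 60 randomized, per arm. Stating power for the logistic model as well is optional and not part of this error.

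The cost is a short replacement text at each place in the next amendment, and a less favourable headline figure. No subjects, tests, endpoints or procedures change.

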14. STUDY CONDUCT

Steps to ensure the accuracy and reliability of data include the selection of qualified investigators and appropriate study sites, review of protocol procedures with the investigator and associated personnel before the study, periodic monitoring visits, and meticulous data management.

14.1. Sponsor and Investigator Responsibilities

14.1.1 Sponsor Responsibilities

The sponsor is obligated to conduct the study in accordance with strict ethical principles (Section 16). The sponsor reserves the right to withdraw a subject from the study (Section 8.3), to terminate participation of a study site at any time (Section 14.7), and/or to discontinue the study (Section 14.6).

Mayne Pharma LLC agrees to provide the investigator with sufficient material and support to permit the investigator to conduct the study according to the study protocol.

14.1.2 Investigator Responsibilities

By signing the Investigator's Agreement (Section 18.1), the investigator indicates that he or she has read the protocol carefully, fully understands the requirements, and agrees to conduct the study in accordance with the procedures and requirements described in this protocol.

The trial will be conducted in accordance with ICH GCP, and the applicable United States (US) Code of Federal Regulations (CFR). The principal investigator will assure that no deviation from, or changes to, the protocol will take place without prior agreement from the Investigational New Drug (IND) sponsor, funding agency and documented approval from the IRB, except where necessary to eliminate an immediate hazard(s) to the trial participants. All personnel involved in the conduct of this study have completed Human Subjects Protection and ICH GCP training.

Investigators should ensure that all persons who are delegated study-related responsibilities are adequately qualified and informed about the protocol, the IP(s), and their specific duties within the context of the study. Investigators are responsible for providing Mayne Pharma LLC with documentation of the qualifications, GCP training, and research experience for themselves and their staff as required by the sponsor and the relevant governing authorities.

To ensure compliance with the guidelines, the study may be audited by an independent person. The investigator agrees, by written consent to this protocol, to cooperate fully with compliance checks by allowing access to all study documentation by authorized individuals.

14.1.3 Confidentiality and Privacy

Participant confidentiality and privacy is strictly held in trust by the participating investigators, their staff, and the sponsor(s) and their interventions. This confidentiality is extended to cover testing of biological samples and genetic tests in addition to the clinical information relating to participants. Therefore, the study protocol, documentation, data, and all other information generated will be held in strict confidence. No information concerning the study or the data will be released to any unauthorized third party without prior written approval of the sponsor.

All research activities will be conducted in as private a setting as possible.

The study monitor, other authorized representatives of the sponsor, representatives of the IRB, regulatory agencies, or pharmaceutical company supplying study product may inspect all

documents and records required to be maintained by the investigator, including, but not limited to, medical records (office, clinic, or hospital) and pharmacy records for the participants in this study. The clinical study site will permit access to such records.

The study participant's contact information will be securely stored at each clinical site for internal use during the study. At the end of the study, all records will continue to be kept in a secure location for as long a period as dictated by the reviewing IRB, institutional policies, or sponsor requirements.

Study participant research data, which is for purposes of statistical analysis and scientific reporting, will be transmitted to and stored at Premier Research. This will not include the participant's contact or identifying information. Rather, individual participants and their research data will be identified by a unique study identification number. The study data entry and study management systems used by clinical sites and by Premier Research staff will be secured and password protected. At the end of the study, all study databases will be de-identified and archived at the Premier Research

14.2. Site Initiation

Study personnel may not screen or enroll subjects into the study until after receiving notification from the sponsor or its designee that the study can be initiated at the study site. The study site will not be authorized for study initiation until:

1. The study site has received the appropriate IRB/IEC approval for the protocol and the appropriate ICF.
2. All regulatory/GCP documents have been submitted to and approved by the sponsor or its designee.
3. The study site has a Clinical Trial Agreement in place.
4. Study site personnel, including the investigator, have participated in a study initiation meeting.

14.3. Screen Failures

Subjects who fail inclusion and/or exclusion criteria may be rescreened for the study. Subjects may only be rescreened once 30 days or more after the original Screening Visit. If a subject is eligible to enter the study after having previously failed screening, the subject will be assigned a new subject identification number.

Screen failures are defined as participants who consent to participate in the clinical trial but are not subsequently randomly assigned to the study intervention or entered in the study. A minimal set of screen failure information is required to ensure transparent reporting of screen failure participants to meet the Consolidated Standards of Reporting Trials publishing requirements and to respond to queries from regulatory authorities. Minimal information includes demography, screen failure details, eligibility criteria, and any SAE.

14.4. Study Documents

All documentation and material provided by Mayne Pharma LLC for this study are to be retained in a secure location and treated as confidential material.

14.4.1 Informed Consent

Consent forms describing in detail the study intervention, study procedures, and risks are given to the participant and written documentation of informed consent is required prior to starting intervention/administering study intervention. The informed consent forms are submitted with this protocol.

Informed consent is a process that is initiated prior to the individual's agreeing to participate in the study and continues throughout the individual's study participation. Consent forms will be IRB-approved and the participant will be asked to read and review the document. The investigator will explain the research study to the participant and answer any questions that may arise. A verbal explanation will be provided in terms suited to the participant's comprehension of the purposes, procedures, and potential risks of the study and of their rights as research participants. Participants will have the opportunity to carefully review the written consent forms and ask questions before signing. The participants should have the opportunity to discuss the study with their family or surrogates or think about it before agreeing to participate. The participant will sign the informed consent document prior to any procedures being done specifically for the study. Participants must be informed that participation is voluntary and that they may withdraw from the study at any time, without prejudice. A copy of the informed consent document will be given to the participants for their records. The informed consent process will be conducted and documented in the source document (including the date) and the form signed before the participant undergoes any study-specific procedures. The rights and welfare of the participants will be protected by emphasizing to them that the quality of their medical care will not be adversely affected if they decline to participate in this study.

14.4.2 Investigator's Regulatory/Good Clinical Practice Documents

The regulatory/GCP documents are listed below.

- Signed original protocol (i.e., Investigator's Agreement)
- Curricula vitae of all investigators and subinvestigators
- Name and address of the laboratories
- List of laboratory reference ranges, and if available, a quality certificate
- Form Signature Log/Delegation of Study-related Duties
- Approved ICF and subject materials
- FDA1572 and financial disclosure forms, as applicable (US sites)
- Any other relevant GCP documents

The regulatory/GCP documents must be received from the investigator and reviewed and approved by Mayne Pharma LLC or its designee before the study site can initiate the study and before Mayne Pharma LLC will authorize shipment of IP to the study site. Copies of the investigator's regulatory/GCP documents must be retained at the study site in a secure location. Additional documents, including a copy of the protocol and applicable amendment(s), the trifarotene (CD5789) Cream IB, eCRF completion guidelines, copies of regulatory references, copies of IRB/IEC correspondence, and IP accountability records should also be retained as part of the investigator's regulatory/GCP documents. It is the investigator's responsibility to ensure that

copies of all required regulatory/GCP documents are organized, current, and available for inspection.

14.4.3 Case Report Forms

By signing the Investigator's Agreement (Section 18.1), the investigator agrees to maintain accurate eCRFs and source documentation as part of the case histories for all subjects who sign an ICF.

Case report forms are considered confidential documents and should be handled and stored accordingly. The sponsor or its designee will provide the necessary training on the use of the specific eCRF system used during the study to ensure that the study information is captured accurately and appropriately.

To ensure data accuracy, eCRF data for individual subject visits should be completed as soon as possible after the visit. All requested information must be entered in the electronic data capture (EDC) system according to the completion guidelines provided by the sponsor or its designee.

The eCRFs must be signed by the investigator or a subinvestigator. These signatures serve to attest that the information contained in the eCRF is accurate and true.

14.4.4 Source Documents

Information recorded in the EDC system should be supported by corresponding source documentation. Examples of acceptable source documentation include, but are not limited to, hospital records, clinic and office charts, laboratory notes, and recorded data from automated instruments, memoranda, and pharmacy dispensing records.

Clinical laboratory data required by the protocol will be electronically transferred from the central/local laboratory to the sponsor or its designee. A paper copy of the laboratory results will be provided to the study site and should be retained with each subject's source data.

14.5. Data Quality Control

Mayne Pharma LLC and its designees will perform quality control checks on this clinical study.

14.5.1 Monitoring Procedures

Mayne Pharma LLC and/or its designee will conduct site visits to monitor the study and ensure compliance with the protocol, GCP, and applicable regulations and guidelines. The assigned clinical research associate(s) (CRA[s]) will visit the investigator and study site at periodic intervals and maintain periodic communication. The investigator agrees to allow the CRA(s) and other authorized Mayne Pharma LLC personnel access. The CRA(s) will maintain current personal knowledge of the study through observation, review of study records and source documentation, and discussion of the conduct of the study with the investigator and staff. While on site, the CRA(s) will review

- regulatory documents, directly comparing entries in the EDC system with the source documents
- consenting procedures
- AE procedures

- storage and accountability of IP and study materials

The CRA will ask for clarification and/or correction of any noted inconsistencies. Procedures for correcting eCRF will be provided to the sites. As representatives of the sponsor, CRAs are responsible for notifying project management of any noted protocol deviations.

By signing the Investigator's Agreement (Section 18.1), the investigator agrees to meet with the CRA(s) during study site visits; to ensure that study staff is available to the CRA(s) as needed; to provide the CRA(s) access to all study documentation, to the clinical supplies dispensing and storage area; and to assist the monitors in their activities, if requested. Further, the investigator agrees to allow Mayne Pharma LLC or designee auditors or inspectors from regulatory agencies to review records and to assist the inspectors in their duties, if requested.

For additional information, please refer to the clinical monitoring plan (CMP).

